Dependent Variables: Hoarding severity (SI-R), Functioning (UPSA, USORT, SLOF, WHODAS 2.0) Independent Variables: Quality of life (Neuro-QoL) Statistical Analysis: The effect of mediator variables will be tested similar to the hypothesis 2.1. **Exploratory Aim 3:** To explore **age and baseline executive functioning** as moderators in order to determine subpopulations in which CREST work best. **Exploratory Aim 4:** To examine time to **maximum effect of treatment gains**.

These aims are focused on exploring on whom and under what conditions the treatment works best. These analyses may identify subpopulations with possibly different mechanisms and must be a baseline or prerandomization characteristic that could impact treatment outcome. We will focus on the moderator effect of age and baseline executive functioning and their interactions with treatment group. Age will be explored as continuous and ordinal (i.e. 45-55, 56-65, 66-75, 76-85) in format. If the interaction effect is significant, pairwise comparisons of groups will be performed. These analyses will examine interactions of group with time at each level of the moderator, and evaluate treatment within each moderator subgroup. These exploratory aims will be examined using random effects regression analyses for each candidate moderator as a main effect and in interaction, similarly to methodology used for the hypothesis testing. Furthermore, we will explore time to maximum effect of treatment gains (>35% reduction on SI-R) using survival analysis. The estimated survivorship curves will be obtained from Kaplan-Meier maximum likelihood estimates for each treatment group. The parameter estimates and 95% CI for the hazard ratio will be obtained from the Cox proportional hazards. Subjects who do not respond to treatment will be censored on their last visit date.

Power Analysis

Power analyses are performed for all hypotheses, incorporating the longitudinal nature of the design. Within this design, repeated observations within subjects are potentially correlated. This has a profound impact on the resulting tests of significance⁹⁸. When the within subject correlation is properly incorporated, the repeated measures analysis takes full advantage of all information obtained from each subject, thereby greatly increasing statistical power over methods that compare treatments cross sectionally⁹⁹. Using the method described by Diggle, Liang, & Zeger¹⁰⁰ and Ahn et al.¹⁰¹, power calculations can be made for repeated measures designs under specified assumptions. Hedeker, Gibbons, & Waternaux¹⁰² extend Diggle et al.¹⁻³'s method for various covariance structures. Procedures describes by Hedeker et al.¹⁰² for Random Regression Models which incorporated these principles was used for the proposed study to estimated needed sample size (RMASS program provided by Hedeker for the Random Regression Model). The design assumptions consist of a 2 treatment groups and up to 7 visits (baseline, sessions 7, 13, 21, 26, and 3- and 6-month follow-up) where the slope is the dependent measure. Other assumptions used were alpha-level, nature of the hypothesis (two-sided versus one-sided), drop-out rate, and variance-covariance matrix of the longitudinal data. We assume a Type-I error level (alpha-level) of .01 to 0.05, drop-out rate of 15% and an autoregressive covariance structure. Data reported in the preliminary studies section which included our own pilot studies were used to calculate effect sizes. From the preliminary analysis of pilot study, the estimated standard deviation (SD) for SI-R score ranges from 12.75-12.82 and the between visit correlation coefficient of 0.71. We considered a range of estimates of stand deviations of 12.5, 12.8 and 13.0, and correlations of .45 to 0.70 in our power analysis. We have reported large effect sizes of 1.02 and 1.51 from our previous studies which converted to differences of 60 to 37 for our primary outcome. However, for these calculations, we conservatively selected smallest clinically meaningful differences that we would like to be able to detect. This was then converted to a medium effect size, defined mathematically as a between-group difference increasing linearly from 0 at baseline to .5 SD units at the last time point. Calculations using the above assumptions indicated that the study will have minimum power of 80% to yield a statistically significant result for a medium effect size with the proposed sample size of 136 patients (68 for each of the two groups).

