Our group has a successful history of recruiting HD patients. Since 2009, we have received over 270 geriatric (over age 60) HD referrals and since 2011 we have received over 125 midlife (under age 60) HD referrals. We have received an increase in calls (7 calls per week) since July 2013 due to our established reputation within the VA Healthcare System and San Diego County. Interestingly, through task force participation and electronic advertisements, we have been able to reach Veterans who were previously not receiving services at the VA and were able to enroll them in our local VA healthcare system. Our funded HD studies within the lab have been completed ahead of schedule due to availability of participants. Thus, we will be able to meet our enrollment goals with our existing recruitment system.

Recruitment targets will be 11-12 patients per study wave (see timeline below) for a total of 136 patients, half of whom will be randomly assigned to CREST. Participants will be administered the Hoarding Rating Scale (HRS)⁶⁹ over the phone by the study coordinator. If they score above a 4 on any item on the HRS, they will be scheduled for an in-person baseline assessment in their home to establish eligibility.

Following informed consent, an independent rater will complete a baseline assessment to determine eligibility. After review of the baseline scores, Drs. [name] and [name] (Co-I) will determine eligibility based on consensus. [name], the study statistician, will prepare the randomization table prior to recruitment of subjects. Subjects will be randomized 1:1 ratio to one of two conditions.

Retention

Our group currently has a markedly low attrition rate for HD studies. We have had 0% attrition across 2 open trials^{15,33} and 8 in our current randomized controlled trial (3 for CREST; 5 for control). Participants will be compensated for their baseline, post-treatment and follow-up assessment points (\$80 total; \$20 per assessment) and a bonus of \$20 for completing all assessments as an additional incentive to participate in treatment. We will optimize follow-up with regular patient contact in treatment, mailings to confirm whereabouts (e.g., birthday and holiday cards), and consent to contact at least one person likely to know subject whereabouts.

Treatment Conditions

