Control Group: Exposure to discarding and acquiring (26 sessions). We propose to use a robust control condition, ET, with the same frequency and amount of therapist contact as CREST. Twenty-six weekly, individual ET sessions (6 months) will be delivered. The control group will receive ET for all 26 sessions and no cognitive training. As in CREST, the ET sessions will be manualized and copies utilized during session by both the patient and therapist.

While we considered using the currently available CBT for HD²¹ as our control condition, ET will allow examination of the specific role that exposure plays in decreasing HD symptoms. Thus, we are investigating

the impact of a concentrated individual component of treatment, which we believe is the true mechanism of HD symptom change. Further, we may find subgroups that benefit from a specific condition, allowing for refinement of future treatment.

Staff

Two part-time PhD-level clinicians experienced in exposure-based treatments will be hired and trained in both CREST and ET. These clinicians will be at the postdoctoral level and license eligible. Study clinicians will rotate on taking new participants. Volunteer research assistants (VRAs) will be utilized as clinician extenders due to the necessity of at-home labor assistance required in cluttered homes. Our lab has a history of recruiting and maintaining VRAs for HD treatment studies and currently has 10 HD clinical VRAs that are approved by our local VA. For the proposed project, a total of 6 clinical VRAs will be trained (see below) along with the clinicians. The VRAs will attend home visits with the study therapists and assist with exposure activities. The VRAs are present during supervision and their work is audiotaped. Two part-time (15 hrs per week) independent raters will be hired to conduct in home assessments throughout the study. One part-time study coordinator/data manager will be hired for the project and assist with phone screening, data organization/entry, and recruitment.

Training and Supervision

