Both the clinicians and VRAs will attend the initial training and weekly supervision. The amount of training and preparation proposed for this investigation is influenced by standard clinical practice within mental health care and consistent with many VA evidence based training roll-outs. The initial 2-day training workshop (8 hours per day) will be provided by [name] and will include review of manuals and homework sheets, videotaped demonstration, and role-played/modeled delivery of CREST and ET. [name] has conducted over 10 HD treatment workshops to mental health clinicians. Weekly 90-minute face-to-face skills based group supervision will be provided by [name]. Supportive coaching, modeling, role-play, review of session audiotapes, and feedback of fidelity ratings will be used in supervision. The type of training program we have designed that places an emphasis on supervision and fidelity is also consistent with training models used for roll out of evidence based practices in large healthcare programs (e.g., VA). Independent raters will receive an initial 2-day training on neuropsychological assessment and ongoing weekly supervision from [name] (Co-I).

Fidelity

In an effort to avoid therapist effects, the therapists will deliver both treatment conditions. While we considered issues of contamination, the cognitive rehabilitation components vary from the exposure sessions thus it would not be intuitive or feasible to deliver rehabilitation modules during the exposure sessions. The ET sessions start with the rationale for exposure and quickly moving to exposure to discarding and not acquiring; leaving no room for teaching compensatory cognitive strategies.

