In the present protocol, we propose to promote and measure treatment fidelity in several ways. First, in addition to training outlined above, study therapists will receive weekly supervision from [name]. Second, therapists will have a checklist to guide them during the conduct of sessions. Third, all sessions of both interventions will be videotaped, and a random sample of 20% of videos from each randomized group will be selected by study statistician, [name], and will be reviewed within a week and rated for treatment fidelity and discriminability by [name] utilizing a standard checklist to document presence of all program elements (See Appendix 3 and 4). We will define therapist compliance as 90% adherence to the items on the weekly checklist. Specific plans have been developed for responding to sub-threshold adherence, ranging from extra training to statistically controlling for adherence to replacing therapists (in the extreme).

With respect to our blind, independent raters, intra-class correlation coefficients (ICC) will used to determine inter-rater reliability of individual items and scale scores for appropriate measurements. We will establish a good inter-rater reliability (ICC=.85) prior to any data collection. Each rater's score will be compared to the "Gold Standard" rater. The raters are required to achieve an ICC of at least .85 for all rating scales. To protect against "rater drift" over the course of the study, all raters will undergo reassessment semiannually. New raters hired during the course of the study will go through the reliability training and testing described above before they rate subjects.

Measures

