At the final stage, hypotheses will be tested using Mixed Effects models, a generalized linear model described by Gibbons et al.⁹¹, Hedeker et al.⁹² and Laird et al.⁹³. Responses at baseline, throughout treatment (sessions 7, 13, 21), post treatment (session 26), 3- and 6-month follow-up will be nested within subjects. Intercept and slope will be modeled as random effects nested within subject; Treatment group, time, and group-by-time interaction will be a fixed effect. A fully saturated treatment by time model will be utilized for inference. Co-variance structure will be chosen based on Akaike's Information Criterion (AIC). Data will be analyzed from all randomized subjects on whom we have a baseline assessment and at least one post-baseline evaluation. If it is needed based on analyses on stage one, baseline covariates (e.g., demographics) will also be added to the model. All hypothesis tests will be intent-to-treat, and will be two-sided at the .05 level. We will adjust p-values for multiple testing within each hypothesis separately by using a Bonferroni correction whenever more than one variable is being tested. Although we didn't have any drop-out in out pilot study, we included a drop-out rate of 10% after the baseline assessment but prior to the first post-baseline evaluation in our power analyses.

Hypothesis 1.1-1.3: Relative to those assigned to ET alone, CREST participants will show significant reduction in **hoarding severity** (primary outcome), improvement in **functioning** (both functional capacity and self-reported functioning; secondary outcomes) and improvement in **quality of life** over time.

- Independent Variables: Treatment Groups (CREST and ET), Time points (baseline, throughout treatment (sessions 7, 13, 21), post-treatment (session 26), 3 and 6-month follow-up).
- Dependent Variable: Hoarding severity (SI-R), Functioning (UPSA, USORT, SLOF, WHODAS 2.0.), Quality of Life (Neuro-QOL).

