- Statistical Analysis: The dependent variable will be analyzed by mixed effects model methods as described above. Baseline demographic and other clinically important characteristics at baseline will be assessed for imbalance between the two groups and their association with the outcome using a univariate analysis. Those found to be significantly unbalanced between intervention groups (p < 0.10) and moderately associated with the outcome (p < 0.15) will be included as covariates in the model. We will adjust p-values for multiple testing within each hypothesis separately by using a Bonferroni correction whenever more than one variable is being tested

Hypotheses 2.1: Treatment adherence, improvement in executive functioning, and reduction in avoidance will mediate hoarding symptom reduction in CREST.

Dependent Variables: Hoarding severity (SI-R)

Independent Variables: Executive Functioning (D-KEFS scaled scores and PCET), Avoidance (AAQ and BAT) and Treatment Adherence score.

Statistical Analysis: The effect of mediator variables will be tested following the procedures recommended by Kraemer⁹⁴, Bauman⁹⁵, Cohen and Cohen⁹⁶, and Busemeyer and Jones⁹⁷. Briefly, treatment mediators explain how or why one variable affects the treatment effect and are defined as mechanisms through which a treatment might achieve its effects. The mediator's effect is measured during the treatment and is correlated with treatment choice and may possibly be a result of treatment and have either a main or interactive effect on the outcome. The dependent or outcome measure (SI-R) will be evaluated throughout the study and will be used as a repeated measure for all the available time points. In essence, the slope of each outcome measure on time will be used as a dependent measure. The mediator and bootstrap technique will be used to calculate a 95% confidence interval for mediation effect. Random effects models will be used for analysis and the change score of mediators will be included in the model.

Hypotheses 2.2: Symptom severity reduction and improved functional capacity will mediate improved quality of life in CREST.

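### Two therapists treat both arms, but therapist is named in neither the randomisation nor the model, so therapist-by-arm balance appears to rest on chance; a fixed therapist term would be a cheap improvement

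*Combined protocol and SAP*

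**What the plan says.** All places are in the combined protocol and SAP.

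- **Staff:** "Two part-time PhD-level clinicians experienced in exposure-based treatments will be hired and trained in both CREST and ET". On how patients reach them: "Study clinicians will rotate on taking new participants". It does not say whether the rotation runs over all participants or within each arm.
- **Fidelity:** "In an effort to avoid therapist effects, the therapists will deliver both treatment conditions". If adherence falls below the threshold, possible responses include adjusting the analysis for adherence and, as a last resort, replacing a therapist. Adjustment for therapist identity is not mentioned.
- **Recruitment and Randomization:** the statistician draws up the table before recruitment, and "Subjects will be randomized 1:1 ratio to one of two conditions". No block size or stratification factor is given.
- **Statistical Plan, final stage:** "Intercept and slope will be modeled as random effects nested within subject; Treatment group, time, and group-by-time interaction will be a fixed effect".
- **Statistical Plan, Hypothesis 1.1-1.3:** covariates enter after a screen: "Baseline demographic and other clinically important characteristics at baseline will be assessed for imbalance between the two groups". A variable must also show some association with the outcome. The screen is described for patient characteristics, so therapist would not naturally enter through it.
- **Power Analysis:** 136 patients, 68 per arm, at least 80% power for a difference that reaches 0.5 SD at the last visit. Therapist is not an input.

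**The concern.** The plan treats therapist effects as a threat worth designing against, and having both therapists deliver both arms is a sound first step. It leaves one thing open. Rotation evens out the size of the two caseloads, but it does not by itself even out the arms within each caseload. If one therapist gets better results and happens to treat more of one arm, part of the arm difference in that trial reflects who delivered the treatment. Without a therapist term, outcome variation between therapists also stays in the error.

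At stake are a little precision and a small chance shift in the estimate. The validity of the test is not in question.

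**Working it through.** **1. The plan's own figure.** As a simple stand-in, take an end-point comparison of two means with a 0.5 SD difference, two-sided alpha 0.05 and 80% power:

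n per arm = 2 × (1.96 + 0.842)² / 0.5² = 62.8, so 63.

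With the 10% dropout in the Statistical Plan, 63 / 0.9 = 70 per arm, or 140 in all. That is within 3% of the stated 136. At 136 with 10% dropout (61.2 per arm) power is 0.790. With the 15% dropout in the Power Analysis section the same calculation gives 150 in all, and power 0.767 at 136. The stand-in is not the plan's slope calculation. It serves here only as a yardstick for changes in power.

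**2. Chance imbalance.** Assume strict alternation (68 patients per therapist) and a 68:68 allocation independent of the rotation. The number X of one therapist's patients who are in CREST is then hypergeometric:

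- Mean 34; variance = 68 × 0.5 × 0.5 × 68/135 = 8.56; SD 2.93; 95% range 28 to 40.
- That therapist's share of the CREST arm minus the share of the ET arm = (2X − 68)/68. Its SD is 2 × 2.93/68 = 0.086, or 8.6 percentage points.
- A gap of 10 points or more has probability 0.23.

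The plan does not describe blocking. With blocks that ignore therapist, still under strict alternation, simulation gives a gap SD of about 12 points for blocks of 2 and 10 points for blocks of 4.

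**3. Shift in the arm difference.** Shift = therapist difference × gap. The documents give no therapist difference, so 0.3 to 0.5 SD is an assumption. SI-R points use an SD of 12.8, from the Power Analysis section.

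| Gap | At 0.3 SD | At 0.5 SD |
|---|---|---|
| 8.6 points (one SD) | 0.026 SD, 0.33 points | 0.043 SD, 0.55 points |
| 17.6 points (40/28 split, edge of the 95% range) | 0.053 SD, 0.68 points | 0.088 SD, 1.13 points |

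For scale, the standard error of the arm difference at 68 per arm is √(2/68) = 0.171 SD, and the planned effect is 0.5 SD.

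**4. Bias and type I error.** The gap is symmetric about zero, so the expected shift is zero. For a therapist difference d, chance imbalance adds d² × 0.086² = 0.0074 d² to the variance of the estimate. Leaving therapist in the error adds (2/68) × d²/4 = 0.0074 d² to the variance that the test uses. The two agree, so the unadjusted test already allows for the imbalance. Simulated type I error was 0.048 to 0.054.

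**5. Power.** Power = Φ(0.5/SE − 1.96). SE² is 2/n with the therapist term and 2/n + (d × gap SD)² without it. The gap SD is 0.086 at 68 per arm and 0.091 at 61.2.

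| Assumed d | 68 per arm: without / with term | 61.2 per arm: without / with term |
|---|---|---|
| 0.2 | 0.827 / 0.830 | 0.786 / 0.790 |
| 0.3 | 0.822 / 0.830 | 0.781 / 0.790 |
| 0.5 | 0.807 / 0.830 | 0.765 / 0.790 |

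The loss runs from 0.4 to 2.5 percentage points.

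**6. What a per-therapist result could show.** With 34 patients per therapist and arm, one therapist's CREST-ET difference has SE √(2/34) = 0.243 SD and a 95% interval of ±0.48 SD. The contrast between the two therapists has an interval of ±1.96 × √2 × 0.243 = ±0.67 SD, wider than the planned effect.

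**The case against.** The best defence is that the design already does the important part. Both therapists treat both arms, so nothing systematic ties therapist to arm, and the remaining imbalance is ordinary chance that the test allows for. The plan also limits variation between therapists: manuals in both arms, shared training, weekly supervision, session checklists, fidelity rating of a sample of videos and a 90% adherence standard. A typical imbalance moves the estimate by far less than its standard error. All of this stands, and it is why the point is minor.

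It is also fair that the concern rests on silence. A reader might infer that rotation and allocation are definitely independent. The documents do not say so: the table could be stratified, or the rotation could run within arm. A reader might also infer that the plan claims to have eliminated therapist effects, but the Fidelity section speaks only of an effort. Nor do the documents support a figure for lopsided caseloads after a therapist is replaced, since replacement appears only as an extreme response with no expected frequency or size.

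What survives is narrow. Supervision and fidelity checks reduce therapist differences but neither balance nor remove them, and adjusting for adherence is not adjusting for therapist. A known two-level factor that the plan itself takes seriously is absent from the stated model.

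**Conclusion.** The point holds as an optional, low-cost improvement. As written, therapist-by-arm balance appears to be left to chance, and the planned model would not absorb an imbalance. For assumed therapist differences of 0.3 to 0.5 SD, a typical gap shifts the arm difference by about 0.03 to 0.04 SD. Over 0.2 to 0.5 SD, leaving therapist out costs about 0.4 to 2.5 points of power. The sample size need not change. These figures rest on strict alternation, an allocation independent of it, and therapist differences that the documents do not supply.

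Two stronger conclusions are not supported. A reader might infer that the CREST-ET comparison is biased or confounded by therapist, but the expected bias is zero and type I error holds. A reader might also infer that balancing or adjusting for therapist would show whether a CREST benefit comes from one therapist's skill with CREST. That is a therapist-by-arm interaction. The balance fix does not address it, and two therapists with 34 patients per cell can neither establish it nor rule it out.

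**What to change.** **Model, at any time before the analysis.** Prespecify therapist and therapist-by-time as fixed effects in the mixed model of the Statistical Plan. The interaction with time does the main work, because a therapist's influence appears as a difference in change. Two therapists are too few to estimate a random therapist effect. Cost: with seven visits as categories, 1 + 6 = 7 parameters, and further terms for any replacement therapist.

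**Randomisation, only if it is not finished.** Assign the next therapist in the rotation once eligibility is confirmed and before the allocation is revealed. Use a separate list per therapist with varying block sizes. Cost: two lists instead of one, and somewhat more predictable allocation, because each therapist sees every assignment on their own list. Varying the block sizes limits this.

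**Reporting, as a separate matter.** Give the CREST-ET difference for each therapist with its interval, labelled as descriptive, and state that it cannot settle whether the effect differs between therapists.

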Demographic and Diagnostic assessment (at baseline only) will assess inclusion criteria, including diagnosis, co-morbidities and cognitive impairment (Table 2). Diagnosis of HD will be assessed using the Structured Interview for Hoarding Disorder (SIHD)⁶⁷, a recently developed but well-validated clinician-administered instrument for diagnosing HD based on the DSM-5 criteria. The SIHD has demonstrated strong inter-rater reliability, convergent validity, and discriminant validity. Potential comorbidities will be assessed with the Mini-International Neuropsychiatric Interview (M.I.N.I.)⁶⁸, a brief diagnostic interview that uses decision-tree logic to assess different mental disorders. This interview has demonstrated excellent reliability and validity (it produces the same diagnoses as the Structured Clinical Interview for DSM-IV Axis I Disorders (SCID-I) or Composite International Diagnostic Interview (CIDI) in 85-95% of cases), and it can be administered much more rapidly than other diagnostic interviews (e.g., SCID-I).

Hoarding symptom severity (primary outcome) will be measured using the Savings Inventory- Revised (SI-R)⁵⁶, a 23-item self-report measure used to assess common hoarding symptoms. Subtests include excessive clutter, compulsive acquisition, and difficulty discarding. The SI-R has demonstrated good internal consistency, divergent validity, concurrent validity, divergent validity, test-retest reliability in clinical samples with hoarding. The total score will be used for analyses.

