Data analysis will be performed in multiple stages. In the initial stage, preliminary analyses will be performed by examination of the distribution of variables to assess their characteristics (means, standard deviations, and skewness). Descriptive statistics and graphs will used to summarize the characteristics of the study population. Continuous measures will be tested for normality and homogeneity of variance. Non-normally distributed variables will be transformed to meet the normal distribution assumption for linear models. Randomization will be assessed by performing a series of Wilcoxon-rank sum tests, Chi-square or Fisher's exact tests to compare the groups on demographic and initial baseline clinical variables. Any variables on which the groups differ initially will be explored as covariates in subsequent analyses, and we will take this into account in the interpretation of the outcome. At the second stage, we will perform sensitivity analyses for the impact that potentially informative missing data may have on the analyses. We will use pattern-mixture models to assess if there is bias due to drop out or missing data. In addition, we will consider the extension of the pattern-mixture model, which allow subject-to-subject heterogeneity.

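### The test-then-transform rule exempts no outcome, so the scale of the primary SI-R group-by-time effect depends on the observed data

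*Combined protocol and SAP*

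**What the plan says.** The initial stage of analysis in the Statistical Plan states: "Continuous measures will be tested for normality and homogeneity of variance". It then states: "Non-normally distributed variables will be transformed to meet the normal distribution assumption for linear models". Both sentences are unconditional and neither exempts an outcome. SI-R is not named there, but it is a continuous outcome of the linear mixed model, so it is covered.

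The plan names no normality test, significance level or unit of testing (visit, arm or all visits together). It also names no transformation, back-transformation or accompanying raw-scale analysis. The only stated level concerns the hypotheses: "All hypothesis tests will be intent-to-treat, and will be two-sided at the .05 level".

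Three other places bear on the scale:

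- Measures, on SI-R: "The total score will be used for analyses".
- Statistical Plan, final stage: "A fully saturated treatment by time model will be utilized for inference".
- Power Analysis: the effect to be detected is "a between-group difference increasing linearly from 0 at baseline to .5 SD units at the last time point", with SI-R SDs of 12.5, 12.8 and 13.0.

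**The concern.** There are two difficulties.

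First, the check is aimed at the wrong object. The mixed model assumes normal residuals and random effects, not normal raw variables. The plan places its check before any model is fitted and describes no residual check. If scores from all visits are looked at together, they mix high pre-treatment with lower later values, and can look non-normal simply because patients improve.

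Second, the result of the check decides the scale of the primary analysis. A group-by-time interaction depends on scale. Suppose one arm falls from 60 to 40 and the other from 63 to 43. Both change by 20 points, so the raw interaction is zero. On the log scale the changes are ln(40/60) = -0.405 and ln(43/63) = -0.382, so the interaction is not zero.

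At stake is whether the primary estimate is in SI-R points, can be set directly against the difference used for power, and is on a scale fixed before the data were seen.

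**Working it through.** **Inputs from the documents.** 136 patients, 68 per arm. Visits: "up to 7 visits (baseline, sessions 7, 13, 21, 26, and 3- and 6-month follow-up) where the slope is the dependent measure". Other design assumptions: "We assume a Type-I error level (alpha-level) of .01 to 0.05, drop-out rate of 15% and an autoregressive covariance structure". SI-R SD 12.5 to 13.0, correlation .45 to .70, effect 0.5 SD at the last visit. At SD 12.8 this is 0.5 × 12.8 = 6.4 points.

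**Step 1. The plan's own power.** Take equally spaced visits (an assumption), equal baseline means and AR(1) correlation matrix V. Let x = 0.5 × (0, 1/6, ..., 1), let q = x′V⁻¹x, and let n = 68 × 0.85 = 57.8 per arm. Power = Φ(√(nq/2) − 1.960).

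- r = .70: q = 0.2717; √(28.9 × 0.2717) = 2.802; power = Φ(0.842) = 80.0%.
- r = .45: q = 0.3408; √(28.9 × 0.3408) = 3.138; power = Φ(1.178) = 88.1%.

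The stated minimum of 80% is reproduced at two-sided .05 on the raw scale. It is not reproduced at alpha .01 (59-71%). The final-stage text gives 10% drop-out rather than 15%; I used 15%.

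**Step 2. How often the rule acts on exactly normal data.** The 5% level is my assumption, as is the rule that any one rejection triggers a transformation.

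| Reading of the rule | Trials in which it acts |
|---|---|
| One test at one visit | about 5% |
| A test at each of seven visits | 1 − 0.95⁷ = 30.2% if independent; 24-33% simulated (Shapiro-Wilk) |
| A test in each arm at each visit (14 tests) | 1 − 0.95¹⁴ = 51.2% if independent; 47-51% simulated |
| All visits stacked, one test | 6-32%, depending on correlation and mean trajectory |

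The simulations used 122 or 136 patients, correlations of about .45 to .70, and AR(1) or exchangeable structure. Other tests move the seven-visit figure somewhat: Jarque-Bera gives 22-26% and D'Agostino 28-32%. The stacked row is not purely a false-alarm rate. Scores pooled over visits with different means are truly non-normal, and the stacked observations are correlated.

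**Step 3. Operating characteristics of a fixed rule.** Simulated trials had N = 136, Shapiro-Wilk at 5% at each visit, and a log or square root applied if any test fired. The comparison was at the last visit, adjusted for baseline. I assumed visit means falling from 60 to 37 and scores bounded at 0 to 92. The figures 60 and 37 stand in Power Analysis, but not as visit means.

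| Correlation .70 | Raw | Log if triggered | Root if triggered |
|---|---|---|---|
| Type I error, AR(1) | 4.3% | 4.3% | 4.5% |
| Type I error, exchangeable | 5.1% | 5.6% | 5.2% |
| Power at 0.5 SD, AR(1) | 84.6% | 82.9% | 84.7% |
| Power at 0.5 SD, exchangeable | 97.3% | 96.7% | 96.9% |

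Simulation error is about 1 point. The largest power loss is 84.6 − 82.9 = 1.7 points.

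**Step 4. What an open choice of scale can do.** In an unadjusted last-visit comparison with 58 per arm and a true 6.4-point difference, raw and log analyses disagree on significance in about 8-9% of trials. With no true difference, taking the best of raw, root and log raises type I error from about 5% to about 6%.

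**The case against.** The case for leaving the rule alone is that it is conventional and does little harm. The initial stage also lists means, SDs, skewness and graphs, so it need not be a mechanical p < .05 trigger. A check within arm and visit would come close to the marginal distribution that the model implies. The powered effect is expressed in SD units, so a standardised effect remains available after transformation. A log is also an unlikely choice for near-normal data, because it creates left skew; the 8-9% disagreement is an illustration and not a forecast. All of this stands, and it keeps the point modest. It does not answer the central difficulty: the text requires transformation, specifies no such within-cell check, and leaves the primary scale open.

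A reader might infer three stronger things that the documents do not support.

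- *That the rule fires on noise in a fixed quarter to a third of trials.* That needs a 5% level, a test at each of seven visits and action on any one rejection. The plan states none of these, and other readings run from about 5% to about 50%.
- *That the trial loses material power.* A log used in every trial does cost power (76% to 72% in an unadjusted last-visit test with 58 per arm). The plan transforms only when a variable is judged non-normal, and then the loss is at most about 2 points.
- *That the rule conflicts with the exploratory analysis of a reduction of more than 35% on SI-R.* The rule concerns linear models. That aim uses Kaplan-Meier and Cox methods, and nothing prevents it from using raw SI-R.

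**Conclusion.** The point holds as a matter of pre-specification and interpretability. The written rule covers the primary outcome, is applied to variables and not to model residuals, and lets the data decide the scale of the group-by-time effect. The power basis, by contrast, is raw SI-R.

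The trigger rate cannot be derived from the documents; the roughly tenfold spread across readings shows that two competent statisticians could follow the rule and analyse SI-R on different scales. A fixed version of the rule is close to harmless for error rates. An unfixed one adds about 1 point of type I error if the most favourable of three scales is taken.

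These sizes rest on normal data, a 5% test, log and square-root transformations and last-visit comparisons, none of which the plan specifies. With about 60 patients per arm, inference on means does not need the transformation. This is a cheap improvement and not a flaw that threatens the trial's validity.

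**What to change.** Replace the transformation sentence in the initial stage of the Statistical Plan with:

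> SI-R total is analysed on its original scale. Normality is assessed on model residuals. If residuals depart from normality, the same model is reported with robust (sandwich) or patient-level bootstrap standard errors, and any transformed SI-R analysis is a sensitivity analysis only. A transformation for a secondary score with marked skew or ceiling is named before unblinding, with the original-scale result also reported.

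The cost is a change of SAP wording and a little more analysis work. The downside is that marked non-normality of SI-R is handled by robust errors and not by reshaping. Judging residuals still involves discretion, but it now affects only the standard errors and not the scale of the estimate. Secondary scores keep room for a transformation, since a score such as U-SORT, which is capped at 42 points, may show a ceiling.
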